#### **5.4 Prior and Concomitant Medications Allowed and prohibited During the Study**

Subjects will be asked to refrain from taking either prescription or OTC medications from the time of Screening until the completion of the study, except for those discussed in this section. All concomitant medications taken during the study will be recorded on the concomitant medications case report form (CRF) with indication for use, totally daily dosage, and dates of drug administration.

Subjects must discontinue use of herbal or over-the-counter medications (with the exception of all medications listed below) for 48 hours prior to treatment days and throughout the study.

##### **Allowed prescription and over the counter medications:**

- Hormone Replacement Therapy (HRT)
- Birth control pills, patches, injections, or implants (all hormonal contraceptives) are allowed provided the dose has been stable for at least one month prior to screening and may be continued throughout the study
- Intermittently used NSAIDS
- Acetaminophen may be administered if medically necessary (not more than 2 g/day)
- Antihistamines

All other concomitant medications will be prohibited, except as specifically exempted by the Sponsor on a case-by-case basis.

##### **Excluded prescription medications:**

Regular or recent intake of prescription drugs, particularly drugs with an influence on blood pressure are excluded.

## **6 STUDY VISIT SCHEDULE AND ASSESSMENTS**

Following review of all Screening procedures, eligible subjects will be enrolled into the dosing phase of the study. The interval between screening and first treatment may be up to 30 days. Eligible subjects will check into the clinic on the day before each treatment and are required to stay approximately 36 hours at the clinic for preparation, dosing and follow-up assessments for each dosing period. The washout period following each dose must be a minimum of 48 hours until the next dose. Subjects will be required to stay in the clinic for the entire duration of the study (unless medically necessary to leave the clinic as instructed by the principal investigator).

All procedure times listed are approximate and are provided as a guide. The PK samples should be drawn as close as possible to the specified time. Vital signs should be taken within a time frame that will allow the PK blood sample to be drawn on schedule. Actual times of procedures for each subject may vary depending on scheduling and will be recorded on the CRF.

Subjects will refrain from smoking or using tobacco products during each clinic stay. Consumption of unsweetened coffee and tea in moderate amounts will be permitted. Breakfast can be served approximately two hours post-dosing, lunch approximately 4-6 hours after dosing and dinner will be served approximately 8-10 hours after dosing.

AEs and concomitant medication usage will be assessed throughout the study from the first day of study patches application until the Final Visit (or Early Termination) procedures are completed.

### **6.1 Screening**

All Screening procedures will be performed after obtaining informed consent and should be completed within 30 days prior to admission for the first of four sequential treatments within the study. Subjects who are not dosed within 30 days after signing the ICF must be re-assessed for eligibility. The screening procedures include:

#### **6.1.1 Screening Visit (Day -30 to -1)**

Subjects who are considered to be good candidates for the study will be seen in the clinic and have the following procedures performed:

- Obtain informed consent
- Obtain a medical history and demographics
- Record concomitant medications
- Perform a physical examination
- Measure Vital signs (inclusive of temperature)
- Measure height
- Measure body weight and calculate BMI
- Confirm eligibility

- Collect blood and urine samples for clinical laboratory tests
- Perform serum pregnancy test (for all females)
- Collect blood for serology (HIV, Hepatitis B, Hepatitis C)
- Perform urine drug and alcohol (breath) testing
- Record a 12-lead ECG

Medical history, physical examination, ECG and laboratory findings are to be reviewed, and eligibility determined. The sponsor must approve any exception to the inclusion or exclusion criteria before planned admission for dosing.

A subject number will be assigned when the subject signs the informed consent. Only subject number, initials and date of birth will identify subjects to the Sponsor. In the event that a subject who has signed the informed consent but did not receive a dose of study medication experiences an SAE, the following information will be captured: demographic data (initials, age, and race), all other Screening assessments that have been completed, AE(s), and concomitant medication(s).

## **6.2 Admission/baseline (Day Before Each Dose)**

If subjects continue to meet all entry criteria the day prior to each dosing, the subject will stay in the clinic overnight. The following procedures will be performed the day prior to each dosing:

- Record concomitant medications
- Perform urine drug and alcohol (breath) testing
- Urine pregnancy test (all women)
- Collect temperature
- Confirm eligibility

Standardized meals and beverages will be served the evening prior to dosing and will be provided by the clinical site. Subjects should complete their dinner by 10 p.m. Subsequently, subjects will fast overnight and receive only clear liquids after 10 p.m.

### **6.3 Study Dosing Days**

#### **General Considerations**

Subjects will fast during the night preceding dosing and until 2 hours after dosing. Water is allowed ad libitum, as well as tea and coffee in moderate amounts.

The following morning (between 0630 and 0930) they will receive that day's scheduled treatment (A, B, C or D). Breakfast should be withheld until two hours post-dosing.

On all study treatment days, an intravenous cannula may be inserted to aid blood sampling. The cannula may be replaced as needed on subsequent study days at the discretion of the Investigator.

All AEs, including any skin irritations and sensations as well as concomitant medication usage will be documented.

When multiple assessments are required at the same time point, they will be conducted in the order as specified in the footnotes of the schedule of events. All procedures should be performed relative to "Time 0" (patch application) when a time is listed.

#### **6.3.1 Dosing Visit (all Periods) – All Treatments**

The following procedures will be performed on each of the four dosing days. The actual procedures will be identical at each of the dosing days, only the study drug administered on each of the treatment days will vary.

##### **6.3.1.1 Pre-Dose - Before treatment Administration on the Day of Dosing**

- Record concomitant medications
- Confirm eligibility
- Measure vital signs
- Record a 12-Lead ECG
- Investigator visual skin and nasal assessment (visual inspection)
- Determine that subject is stable and in good health and appropriate for dosing
- Collect blood for a PK sample within 15 minutes prior to administering study drug

### **6.3.1.2 Treatment Administration (t = 0)**

- Apply patches or administer intranasal zolmitriptan (see [Appendix 1](#) for instructions on patch administration)
- Begin recording all AEs, whether observed by investigator, reported by the subject, observed in laboratory findings, or discovered by other means, on the AE CRF through the End of Study (or Early Termination) final visit. All adverse events must be followed to resolution.
- Record patch adhesion score

### **6.3.1.3 2 Minutes after Treatment Administration**

- Collect blood for a PK sample
- Record concomitant medications

### **6.3.1.4 5 Minutes after Treatment Administration**

- Collect blood for a PK sample
- Record concomitant medications

### **6.3.1.5 10 Minutes after Treatment Administration**

- Collect blood for a PK sample
- Measure vital signs
- Record concomitant medications

### **6.3.1.6 15 Minutes after Treatment Administration**

- Collect blood for a PK sample
- Record a 12-Lead ECG
- Record concomitant medications

### **6.3.1.7 20 Minutes after Treatment Administration**

- Collect blood for a PK Sample
- Record concomitant medications

### **6.3.1.8 30 Minutes after Treatment Administration**

- Collect blood for a PK sample
- Record concomitant medications and adverse events
- Record patch adhesion score
- Remove patches and perform the following procedures in the order listed below (for 30 minute wear time treatment assignment only):

- Investigator visual skin assessment of the patch application sites
- Retain and package patches for freezing. Refer to full instructions in [Appendix 3](#).
- Application site swabbing. Refer to full instructions in [Appendix 3](#).

#### **6.3.1.9 45 Minutes after Treatment Administration**

- Collect blood for a PK sample
- Record concomitant medications

#### **6.3.1.10 60 Minutes after Treatment Administration**

- Collect blood for a PK sample
- Measure vital signs
- Record a 12-lead ECG
- Record concomitant medications and adverse events
- Record patch adhesion score (60 minute wear time assignment only)
- Remove patches and perform the following procedures in the order listed below (for 60 min wear time assignment only):
  - Investigator visual skin assessment of the application sites
  - Retain and package patches for freezing. Refer to full instructions in [Appendix 3](#).
  - Application site swabbing. Refer to full instructions in [Appendix 3](#).

#### **6.3.1.11 90 Minutes after Treatment Administration**

- Collect blood for a PK sample
- Record concomitant medications

#### **6.3.1.12 Two Hours after Treatment Administration**

- Collect blood for a PK sample
- Measure vital signs
- Record concomitant medications

#### **6.3.1.13 Four Hours after Treatment Administration**

- Collect blood for a PK sample
- Measure vital Signs
- Record concomitant medications

#### **6.3.1.14 Eight Hours after Treatment Administration**

- Collect blood for a PK Sample

- Record a 12-Lead ECG
- Record concomitant medications

#### **6.3.1.15 Twelve Hours after Treatment Administration**

- Collect blood for a PK Sample
- Measure vital Signs
- Record a 12-Lead ECG
- Determine if subject is stable for the next dosing period
- Investigator visual skin assessment of the application sites
- Perform a physical examination
- Record concomitant medications and adverse events

#### **6.3.1.16 Twenty Four Hours after Treatment Administration**

- Collect blood for a PK Sample
- Record concomitant medications and adverse events
- Investigator visual skin assessment of the application sites

#### **6.3.1.17 Zolmitriptan PK Sample Handling**

Details related to zolmitriptan PK sample collection and shipment is provided in [Appendix 2](#).

#### **6.4 End of Study Visit/or Early Termination**

- Within 48 hours after completion of all protocol required procedures on the last dosing day, subjects will complete an End of Study Visit. At that time, the following assessments will be performed:
- Record all AEs, whether observed by investigator, reported by the subject, observed in laboratory findings, or discovered by other means, on the AE CRF through the end of study final visit.
- Record a 12-Lead ECG
- Record any new concomitant medications and adverse events
- Measure vital signs (inclusive of temperature)
- Perform a physical examination
- Measure body weight
- Investigator visual skin assessment of the application sites
- Collect blood and urine for laboratory tests and serum pregnancy test (for all females)
- Dismiss subject from the study

#### **6.5 Post Study Phone Call - Follow-up on Adverse Events**

Subjects must be called within 5-10 days following the day of discharge to follow-up on resolution of all ongoing AEs.

#### **6.6 Early Termination**

Subjects who terminate early will complete the assessments normally scheduled for the End of Study Visit (see above).

## 7 STUDY PROCEDURES

### 7.1 General Confinement Restrictions

Alcohol is prohibited 24 hours before study drug administration until discharge from the clinic.

Subject will not engage in any activity that may cause inflammation, irritation, sunburn, lesions or tattoos at the intended application sites from 2 weeks prior to Screening through their last day of study participation. Subject will not engage in strenuous activity at any time during their stay at the clinical unit. Subjects will be required to stay in the clinic for the entire duration of the study (unless medically necessary to leave the clinic as instructed by the principal investigator).

### 7.2 Collection, Processing and Assay of Samples

Blood sampling will be performed at several close time points throughout the study therefore the study center may utilize an IV cannula. After blood sampling, the cannula will be flushed with saline.

Each of the plasma samples collected for pharmacokinetic analysis will be separated into two containers. One of the samples will be sent to the analytical laboratory for analysis and one sample will be maintained at the investigative site. The plasma sample retained at the site may be used for further analysis (additional metabolites, etc.) at some future timepoint.

Subjects who complete all four treatments will have a blood draw volume of approximately 395 mL for the entire duration of the study (See Table below).

#### Blood Volume Requirements (mL)

Purpose	Expected Number	Sample Amount (in mL)	Total Amount (in mL)
Clinical laboratory tests (blood chemistry)	2	8.5	17.0
Hematology and Serum Pregnancy	2	4.0	8.0
PK	60 (15 samples per period x 4 periods)	4.0	240.0
	60 (discard volume with cannula flush)	2.0	120.0
Serology (screen only)	1	10.0	10.0
GRAND TOTAL			395 mL

### 7.3 Assessment Details

#### 7.3.1 Clinical Laboratory Tests

Standard clinical laboratory tests (serum pregnancy for all women, CBC, hematology, and urinalysis) will be performed at Screening and End of Study (or early termination) and urine pregnancy testing for all women at each Admission/baseline visit.

A blood sample at screening will be taken to perform serological tests for HIV, Hepatitis B and Hepatitis C.

CBC will include the following: Hematocrit, hemoglobin, red blood cell count, white blood cell count with differential, platelets, mean corpuscular volume, mean corpuscular hemoglobin, and mean corpuscular hemoglobin concentration.

Blood hematology will include the following: Urea, glucose, aspartate aminotransferase (AST), alanine aminotransferase (ALT), alkaline phosphatase (AP), lactate dehydrogenase (LDH), sodium, phosphate, potassium, chloride, creatinine phosphokinase (CPK), globulin, cholesterol, creatinine, serum calcium, total bilirubin, triglyceride, cholesterol (HDL and LDL), gamma glutamyl transpeptidase (GGT) and uric acid.

Urinalysis will include the following: bilirubin, blood, glucose, ketones, leuokocyte esterase, nitrite, pH, protein, specific gravity, and urobilinogen. Microscopic examination will be conducted if protein, leukocyte esterase, nitrite and/or blood are detected.

Urine drug screen and alcohol (breath) testing will be performed at screening and each Admission/baseline visit. Urine drug screen will test for amphetamine, barbituates, cocaine, cannabinoids, phencyclidine (PCP), opioids, and methamphetamines.

Samples will be analyzed by a local laboratory. After reviewing the laboratory reports and evaluating the results, the Investigator must review, sign/date the laboratory report.

#### 7.3.2 Vital Signs

Vital signs include heart rate, pulse, respiratory rate, as well as systolic and diastolic arterial pressure. Vital signs will be recorded after subjects have been in the seated resting position for 2 minutes. Temperature will be taken at Screening, admission/baseline, and at end of study visit/or early termination only.

#### 7.3.3 Electrocardiograms

A standard 12-lead ECG will be performed by a qualified individual at the site. General morphology and intervals [Heart rate, QRS, PR interval, QRS, QTn, QTcf], of interest will be assessed with each tracing. The principal or sub-investigator must review the tracing and assess it for any clinically significant abnormality. Any clinically significant abnormality noted at the time of screening on the ECG will be recorded in the appropriate source document and may result in the exclusion of the subject from the study.

### **7.3.4 Investigator Visual Skin Assessments of the Application Sites**

Each M207 patch site (where a patch has been removed) will be observed for the following skin assessments pre-dose and immediately after removal of the patches from the subject's skin (and before swabbing) at 30 min (for 30 min wear time treatment groups only), 60 min, 12 hr, 24 hr and at the End of Study/or Early Termination visit.

#### **7.3.4.1 Erythema**

The erythema evaluations will be performed using the following scale:

- 0 = None
- 1 = Mild redness
- 2 = Moderate colored redness
- 3 = Beet colored redness

#### **7.3.4.2 Edema**

The edema evaluations will be performed using the following scale:

- 0 = None
- 1 = Slight edema
- 2 = Moderate edema
- 3 = Severe edema

#### **7.3.4.3 Bruising**

Bruising assessments (visual rating) will be performed using the following scale:

- 0 = None
- 1 =  $\leq 25\%$  application site has bruising spots
- 2 =  $\geq 26$  to  $\leq 50\%$  application site has bruising spots
- 3 =  $> 50\%$  application site has bruising spots

#### **7.3.4.4 Bleeding**

Bleeding will be assessed using the following scale:

- 0 = None
- 1 = Pink color on skin
- 2 = Visible blood drop
- 3 = Active bleeding

### **7.3.5 Residual Drug on Used M207 Patches**

The used patches should be placed in the proper cryovial tube provided by Zosano and immediately placed on dry ice or frozen at approximately -80°C (plus or minus 10°C) and kept frozen until shipment to the bioanalytical lab. Used patches may be assayed for residual zolmitriptan if considered relevant after review of the pharmacokinetic results. Instructions for removing and storing the patches are provided in [Appendix 3](#).

### **7.3.6 Residual Drug on Skin after M207 Patch Removal**

At the time patches are removed (for all patch treatment groups), the M207 patch skin sites will be swabbed to collect any residual drug that may be on the skin surface where a transdermal M207 patch has been applied. The process consists of using 3 swabs to capture the drug residual for each patch site. The procedure is described in [Appendix 3](#).

### **7.3.7 Patch Adhesion Assessment**

For each assessment, investigators should use a 5-point numerical scale in which each score corresponds to a specified range of adhered surface area of each patch, as follows:

0 =  $\geq 90\%$  adhered (essentially no lift off the skin)

1 =  $\geq 75\%$  to  $< 90\%$  adhered (some edges only lifting off the skin)

2 =  $\geq 50\%$  to  $< 75\%$  adhered (less than half of the patch lifting off the skin)

3 =  $> 0\%$  to  $< 50\%$  adhered (not detached, but more than half of the patch lifting off the skin without falling off)

4 = 0% adhered (patch detached; completely off the skin)

### **7.3.8 Recording Adverse Events**

Adverse events are collected from the time of first patch application until the end of the study. A detailed discussion regarding the collection and reporting of adverse events is provided in [Section 8](#).

## 8 ADVERSE EVENTS

All skin and systemic AEs, regardless of treatment group or suspected causal relationship to the investigational products, will be reported as described in the following sections.

For all AEs, the Investigator must pursue and obtain information adequate both to determine the outcome of the AE and to assess whether it meets the criteria for classification as a SAE requiring immediate notification of the Sponsor. For all skin and AEs, sufficient information should be obtained by the Investigator to determine the causality of the AE. The Investigator is required to assess causality. For skin and systemic AEs with a causal relationship to the investigational product, follow-up by the Investigator is required until the event or its sequelae resolve or stabilize at a level acceptable to the Investigator, and Zosano Pharma concurs with that assessment.

### **Reporting Period**

Collection of skin and systemic AEs will be initiated from the time of treatment application and will conclude when the end of study procedures for the fourth treatment are completed (or Early Termination). The Investigator will also report to the Sponsor all SAEs that come to his/her attention after the study termination within 30 days of the last dose of study drug.

Any SAE occurring any time after the reporting period must be promptly reported if a causal relationship to the investigational product is suspected.

#### **8.1 Adverse Event Definitions**

An AE is any untoward medical event that occurs in a clinical investigation, where a subject is administered a product or medical device, without regard to causal relationship between the event and the treatment. An AE can be any unfavorable and unintended sign or symptom, including clinically significant laboratory values and test results, concomitant illness, accident, or worsening of an existing medical condition.

Information about all adverse events, whether volunteered by the subject, discovered by investigator questioning, or detected through physical examination, laboratory or other means, will be collected and recorded on the Adverse Event CRF using the signs, symptoms or diagnosis associated with them and followed until resolution or, in the Investigator's opinion, a stable condition is reached, or until the patient is lost to follow up.

Medical conditions/diseases present before starting study treatment are only considered adverse events if they worsen after starting study treatment.

In the event of a clinically important AE, a serum sample may be collected as soon as possible after the occurrence of the event for drug assay or for additional laboratory tests. The Investigator will ensure that the serum sample is properly labeled and stored. The Investigator and other study personnel responsible for the care of the patient will institute any supplementary investigations of significant AEs based on the clinical judgment of the likely causative factor(s). This may include seeking further opinion of a specialist in the field of the AE.

Any abnormal lab tests starting from the day of study patch application that are clinically significant, as determined by the Investigator, should be reported as AEs if:

- the test result is associated with accompanying symptoms;
- the test result requires additional diagnostic testing or medical/surgical intervention;
- the test result leads to a change in study dosing or discontinuation from the study, significant additional concomitant drug treatment, or other therapy;
- the test result is considered to be an AE by the Investigator or sponsor

Merely repeating an abnormal test, in the absence of any of the above conditions, does not constitute an AE. Any abnormal test result that is determined to be an error does not require reporting as an AE.

## **8.2 Documentation and Reporting of Adverse Events By the Investigator**

All adverse events (AEs) occurring after the application of the first dose through the End of study visit/or early termination, will be reported on the AE CRF pages. Based on the medical judgement of the investigator, all non-serious systemic and skin AEs will be followed until 30 days after the final end of study visit. All non-resolved, non-serious systemic and skin AEs beyond such date will be recorded as 'ongoing' without further follow up.

However, an AE form will not be filled out for subjects who sign the ICF but fail the entry criteria (Screening failures) during the Screening process and experience a non-serious AE.

Application site reactions will be reported on a dedicated assessment form for the visual skin assessment of the application sites. The regular AE form does not have to be completed for such events unless the events are not covered by the questions on the visual skin assessment form or are reported outside their time window. However, all such events will be included in the analyses of adverse event incidence.

Each AE, including skin AEs, is to be assessed to determine if it meets the criteria for an SAE. If an SAE occurs, expedited reporting will follow local and international regulations, as appropriate (See [Section 8.4](#)). It should be noted that the form for collection of SAE information is not the same as the AE CRF. Where the same data are collected, the forms must be completed in a consistent manner. For example, the same AE term should be used on both forms. Systemic and skin AEs should be reported using concise medical terminology on the CRF pages as well as on the form for collection of SAE information.

In addition to recording the signs, symptoms or diagnosis associated with them to describe the adverse event, the following will also be assessed and recorded:

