### 8.2.3 Relationship to Study Drug

The Investigator's assessment of causality must be provided for all systemic and skin AEs (serious and non-serious). An Investigator's causality assessment is the determination of whether there exists a reasonable possibility that the investigational product caused or contributed to an AE. If the Investigator's final determination of causality is unknown and the Investigator does not know whether or not the investigational product caused the event, then the event will be handled as "related to investigational product" for reporting purposes. If the Investigator's causality assessment is "unknown but not related to investigational product", this should be clearly documented on study records.

In addition, if the Investigator determines an SAE is associated with study procedures, the Investigator must record this causal relationship in the source documents and CRF, as appropriate, and report such an assessment in accordance with the SAE reporting requirements, if applicable.

After careful medical consideration, the Investigator will evaluate the relationship of each AE to study drug applying the following definitions:

**Probably Related:** An AE that is likely due to the use of the study drug. The relationship in time may be suggestive. An alternative explanation is less likely, e.g., concomitant drug(s), concurrent disease(s).

**Possibly Related:** An AE that may or may not be due to the use of the study drug. The relationship in time is reasonable; therefore, a causal relationship cannot be excluded. An alternative explanation is inconclusive, e.g., concomitant drug(s), concurrent disease(s).

**Not Related:** An AE that is judged to be clearly due only to extraneous causes (disease, environment, etc.). The cause must be noted on the AE CRF page.

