#### **16.1 Adverse Events**

Adverse events (AEs) will be mapped to preferred term and body-organ system using MedDRA™. The number and percentage of subjects reporting AEs will be

summarized by AE preferred term and AE body-organ system. Adverse events will be summarized by severity and relationship to study drug also.

In particular, AE summary tables will be presented for the following:

- AE overview
- AE incidence
- AEs by severity
- AEs leading to study drug discontinuation
- AEs by relationship

Each participant will be counted only once within each summation level (SOC; preferred term). If a participant experiences more than one AE within each summation level only, the AE with the strongest relationship or the maximum severity, as appropriate, will be included in the summaries of relationship and severity.

Adverse events will be attributed to the most recent dose taken, i.e., AEs occurring post-dose but prior to the next dose, will be attributed to the most recent dose by using the date and time the AE occurred. Adverse events occurring after the first dose of study drug are considered treatment emergent.

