**Summary Table 14.3.1.1: Overview of Adverse Event**

	Treatment			
	Treatment (A)	Treatment (B)	Treatment (C)	Treatment (D)
subjects who received study treatment				
subjects who discontinued due to AEs				
subjects with at least one AE				
Total number of AEs				
Total number of SAEs				
Source: Appendix 16.2.1 and 16.2.7				

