**Listing 16.2.8.7: Listing of Adhesion Assessment at 30 Minute and 60 Minute**

Subject	Patch	Adhesion Assessment Time Point	Adhesion Assessment Date (DDMMYYYY)	Adhesion Assessment Time (HH:MM)	Adhesion Assessment Score	Adhesion Assessment Result
XXXX						

**Listing 16.2.8.8: Listing of Investigator Visual Skin Evaluation at Pre-dose, 30 Minute, 60 Minute, 12 hour, 24 hour and EOS/Early Term**

Subject	Patch Site	Visual Skin Assessment Time Point	Visual Skin Assessment Date (DDMMYYYY)	Visual Skin Assessment Time (HH:MM)	Visual Skin Evaluation	Visual Skin Evaluation Score	Visual Skin Evaluation Result
XXXX					Erythema Evaluation		
					Edema Evaluation		
					Bruising Assessment		
					Bleeding Assessment		

**Listing 16.2.8.9: Listing of ECG performed on during Screening, Pre-dose, 15 minutes, 60 minutes, 8 hour, 12 hour and End of Study**

Subject	Date of ECG performed (DDMMYYYY)	Time of ECG performed (HH:MM)	ECG Parameters (unit)	Result	Overall Interpretation	If Abnormal, Clinically significant?	If Yes, please specify
XXXX			Heart Rate (beats/min)				
			PR Interval (msec)				
			QRS Interval (msec)				
			QT Interval (msec)				
			QTcF - Fridericia's Correction Formula (msec)				

Figure 1: Linear Mean Plot of Zolmitriptan Treatments over Time

[figure not shown]

Figure 2: Mean Plot of Zolmitriptan Treatments over First 2 Hours

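### Protocol 8.2 counts every application-site reaction in AE incidence, but SAP 16.1 has no step to bring in those recorded only on the skin form, which would mainly understate incidence for the patch treatments

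*Protocol*

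**What the plan says.** Protocol 8.2 makes three linked statements about application-site reactions.

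- They are reported on a dedicated form for the visual skin assessment.
- "The regular AE form does not have to be completed for such events", unless the skin form's questions do not cover the event or it falls outside the form's time window.
- "However, all such events will be included in the analyses of adverse event incidence".

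Other parts of the protocol point towards the AE form. Section 8.1 says that information on all adverse events "will be collected and recorded on the Adverse Event CRF", and the opening of 8.2 and Sections 6.3.1.2 and 6.4 say much the same. Section 8.2.3 adds that the investigator's "assessment of causality must be provided for all systemic and skin AEs".

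SAP 16.1 maps adverse events to MedDRA terms and counts subjects by term and body system. It adds: "Adverse events will be summarized by severity and relationship to study drug also". It does not mention the skin form. The source line of mock Table 14.3.1.1 reads "Source: Appendix 16.2.1 and 16.2.7", that is, the disposition and AE listings. Skin-form data go to Listing 16.2.8.8 ("Listing of Investigator Visual Skin Evaluation at Pre-dose, 30 Minute, 60 Minute, 12 hour, 24 hour and EOS/Early Term") and, under SAP 16.4, to score tables by treatment (Tables 14.3.5 and 14.3.6).

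**The concern.** The protocol makes a commitment about how an endpoint is counted, and the analysis plan has no means of keeping it. AE incidence is the first safety endpoint in Protocol 4.2, and comparing the tolerability of M207 with the spray is the third objective.

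The gap is not even-handed. The skin form exists for M207 patch sites (Protocol 7.3.4), and no comparable form replaces the AE form for nasal reactions to the spray. Events caused by the patch can therefore go missing by this route, while events caused by the spray cannot. An error in that direction flatters the investigational product in the AE tables.

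A programmer who knows the Protocol 8.2 rule still could not apply it without deciding which scores are events and what to call them. In an open-label study those choices should not be left until the data are in hand.

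**Working it through.** The documents give no figure to reproduce: there is no formal sample size calculation and no application-site reaction rate. The check is mainly a comparison of texts.

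**1. Can the skin listing feed the AE tables?** Mock listings in the SAP:

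| Needed by the AE tables | AE listing 16.2.7 | Skin listing 16.2.8.8 |
|---|---|---|
| Preferred term (14.3.1.2 to 14.3.1.4) | yes | no; scale name only |
| AE severity (14.3.1.3) | yes | no; 0 to 3 score |
| Relationship to drug (14.3.1.4) | yes | no |
| Onset, for attribution to a dose | yes | assessment date and time only |

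The 0 to 3 skin scores cannot stand in for AE severity. Protocol 8.2.2 defines severity by discomfort, effect on daily activities and need for intervention. Neither SAP 16.1 nor Protocol 10.5 gives a score threshold, a preferred term, an onset rule or a rule against double counting.

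**2. Double counting.** SAP 16.1 says "Each participant will be counted only once within each summation level". That protects subject counts. It does not protect the totals of AEs in Tables 14.3.1.1 and 14.3.1.2 if a reaction appears on both forms.

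**3. Attribution.** SAP 16.1 assigns each AE to the most recent dose. The sequences are ABCD, BDAC, CADB and DCBA with equal allocation (SAP 4.1), so 24/4 = 6 subjects have D last. Application sites are scored again at the End of Study visit (Protocol 6.4). In sequence ABCD, a patch-site reaction first scored at that visit would go to D under the SAP rule. If such events are left out, D loses one. If they are brought in without a new attribution rule, the spray is charged with a patch reaction.

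**4. Size.** Let k be the number of subjects in one treatment whose only event is a skin-form-only reaction. With n = 24 per treatment, the loss in overall AE incidence is k/n. The values of k are assumptions.

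| k | k/24 | Loss (percentage points) |
|---|---|---|
| 0 | 0/24 | 0 |
| 1 | 1/24 | 4.2 |
| 3 | 3/24 | 12.5 |
| 6 | 6/24 | 25.0 |

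A subject who has another AE in the same treatment stays in the overall count, but is still missing from the row for the skin term and from the total number of AEs.

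**The case against.** The strongest reply has four parts.

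- **Silence is not exclusion.** SAP 16.1 speaks of adverse events without limiting them to those on the AE form. Listing 16.2.7 carries no such limit either, only Table 14.3.1.1 has a source line, and the SAP allows mock tables to be modified. This stands as far as it goes: nothing forbids including the reactions. But nothing says how to, and permission to change a table does not supply a threshold, a term or a causality rule.
- **The AE form may be completed anyway.** Protocol 6.3 asks that all AEs, including skin irritations, be documented. Sections 6.3.1.2, 6.4 and 8.1 direct AEs to the AE CRF. AE recording is also scheduled at 30 and 60 minutes, 12 hours and 24 hours, when skin is assessed. This stands and makes the loss conditional. It does not remove it, because the specific sentence in 8.2 lets a compliant site omit the AE form.
- **The skin CRF is not in the documents.** That severity and causality are not collected for skin-form-only events is inferred from a mock listing. This stands, and it bears on the cost of the fix.
- **The consequence is limited.** No AE test or decision threshold is planned, and erythema, edema, bruising and bleeding are reported by treatment and time. This also stands. The score tables do not, however, provide the AE incidence that Protocol 8.2 calls for, and they offer no comparison with D.

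**Conclusion.** The two documents disagree, and the SAP should be corrected before database lock. Run as written, it omits skin-form-only reactions from the AE tables, contrary to Protocol 8.2. The omission would mainly lower incidence for A, B and C relative to D. The cost is 4.2 points per affected subject in a treatment of 24; the number affected is unknown and may be zero.

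Three stronger readings are tempting, and the documents do not support them.

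- *The spray can never lose an event this way.* It can, in sequence ABCD, under the most-recent-dose rule. The direction is predominant, not absolute.
- *The AE comparison is biased by a material amount.* No reaction rates are given, and several protocol sections also call for the AE CRF. Only the possibility and its main direction can be stated.
- *Skin tolerability information is lost.* It is not. SAP 16.4 and Tables 14.3.5 and 14.3.6 report it, so the arm-versus-thigh irritation comparison is largely served. The fault is confined to the AE tables.

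**What to change.** Add to SAP 16.1:

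- Application-site reactions recorded only on the visual skin assessment form (Listing 16.2.8.8) are counted in the AE incidence tables, as Protocol 8.2 requires. A reaction that is also on the AE form is counted once, in event totals as well as subject counts.
- Each such reaction is attributed to the treatment applied at that site, not to the most recent dose. A and C both use the upper arm, so the site record must carry the treatment or period.
- Onset is the first observed post-dose score that qualifies. Scores filled in by the last-observation-carried-forward rule in SAP 7.0 are not used.

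Before database lock, the sponsor and investigator should set which scores relative to pre-dose count as an event, the preferred term for each scale, and the severity and causality rule. Show AE incidence with and without these events, and add Listing 16.2.8.8 to the source line of Table 14.3.1.1.

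The alternative is to amend Protocol 8.2 so that the two documents agree. Under Protocol 11.1 that needs sponsor and IRB/IEC approval unless the change is administrative.

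The SAP route costs some wording, a small derivation and one extra set of AE rows, with no new visits or samples. Site queries or a CRF change may be needed if severity and causality were not collected for these reactions. M207 AE counts may look higher, which is the reason for showing incidence both ways.
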